5.0 ANALYSIS POPULATIONS

Three populations are defined for the study. Intent-to-treat (ITT) population will consist of all subjects who receive study drug and provide some post baseline efficacy values. Completer population will include all subjects who complete the study. The primary efficacy analyses will be based on the Completer population. Safety population will include all subjects who receive study drug. All safety analyses will be based on the Safety population.

6.0 GENERAL CONVENTIONS

Unless otherwise stated, all analyses will be performed using SAS Version 9 and all hypothesis tests will be conducted at a two-sided significance level of 0.05. P-values will be presented with 3 decimals and p-values that are less than 0.001 will be presented as <0.001.

Continuous (non survival related) data will be summarized using descriptive statistics: number of observations (n), mean, standard deviation (SD), median, minimum, and maximum. Frequencies and percentages will be used to summarize categorical (discrete) data. Presentations of categorical data will generally suppress percentages for items where the count is zero in order to draw attention to the nonzero counts. In general, mean, standard deviation, median, minimum, maximum, and percentages will be presented with one decimal.

Unless otherwise stated, confidence intervals, when presented, will be constructed at the two-sided 95% level.

Summaries of plasma concentrations of BPN and norbuprenorphine will be presented for the Completer population by treatment group. The following descriptive statistics will be presented at each nominal time point: n, arithmetic mean, SD, coefficient of variation percentage (CV%), median, geometric mean, geometric CV%, minimum and maximum values. Individual plasma concentrations of BPN and norbuprenorphine will be listed for the Safety population by treatment group. Mean plasma concentration-time data will be displayed for the Completer population in linear and semi-logarithmic scales.

The pharmacokinetic parameter data will be listed and summarized by treatment for the Completer population. Summary statistics will include n, arithmetic mean, SD, CV%, median, geometric mean, geometric CV%, minimum and maximum values.

Data listings will present all data collected on CRFs by study drug, center, and subject number.

6.1 DEFINITION OF BASELINE

Unless otherwise stated, the last observed measurement prior to or on the date of randomization will be considered the baseline measurement. If multiple observations are made during baseline, the baseline will be defined as average of the observations obtained during the baseline phase.

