#### 7.1.3. Treatment Phase

#### 7.1.3.1. Days 0 to 6

On the morning of Day 0 of the Treatment Phase, subjects will receive one of the following treatments (based on randomization in a 1:1 ratio, stratified by gender) to:

- Group A: CAM2038 q1w 24 mg SC injection
- Group B: CAM2038 q1w 32 mg SC injection

Maintenance IR morphine 30 mg will be withheld for at least 12 hours prior to CAM2038 q1w dosing; therefore, the Day -1 evening dose and the Day 0 morning dose of IR morphine 30 mg will be withheld. The Clinical Opiate Withdrawal Scale (COWS; See Section 17.2) will be administered prior to dosing with CAM2038 q1w; in order to be dosed on Day 0, subjects will be required to have a COWS score of  $\geq 8$ , indicative of mild withdrawal.

CAM2038 q1w treatment will be administered at approximately 9:00 am; CAM2038 q1w administration instructions for user (IFU) will be provided in the Manual of Procedures (MOP).

On Days 1 to 3 and Days 4 to 6, subjects will undergo 2 separate Hydromorphone Challenge Sessions (described in Section 7.1.4), with each daily challenge dose of IM hydromorphone administered at approximately 9:00 am (i.e., approximately 24, 48, 72, 96, 120, and 144 hours following Day 0 CAM2038 q1w injection). Safety and pharmacodynamic assessments will be conducted immediately following each dose of hydromorphone administered in each Hydromorphone Challenge Session (maximum 5 hours after Hydromorphone Challenge Session). Plasma samples will also be collected prior to hydromorphone dosing on each day of the Hydromorphone Challenge Sessions.

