Before each scheduled IR morphine 30 mg dose is administered, research/nursing staff will record oxygen saturation and respiratory rate and assess the subject for sedation and/or intoxication. If respiratory rate drops to <12 breaths per minute or oxygen saturation is <95%, the measurements will be repeated and recorded. If either oxygen saturation or respiratory rate remains outside parameters or the subject appears sedated or intoxicated, the oral maintenance dose will be withheld and a study Investigator notified. The withheld dose may be administered later (and the administration time recorded) once it is determined that the subject's status has returned to within a safe range. Continuous pulse oximetry and telemetry can be implemented at the Investigator's discretion.

m Pulse oximetry/Cardiac monitoring/Respiratory rate monitoring will be included on each Hydromorphone Challenge Session day (i.e., Days -3, -2, -1, 1, 2, 3, 4, 5, 6, 8, 9, 10, 11, 12, and 13). Monitoring will be continuous from pre-dose up to 5 hours post-dose or longer, if clinically indicated. After each dose of hydromorphone, subject's oxygen saturation, respiratory rate, and overall safety profile will be reviewed by the research/nursing staff to determine whether it is safe to proceed with administration of the next dose of hydromorphone.

<sup>n Includes temperature, blood pressure, pulse rate, respiratory rate.

On each Hydromorphone Challenge Session day (i.e., Days -3, -2, -1, 1, 2, 3, 4, 5, 6, 8, 9, 10, 11, 12, and 13), vital signs will be collected predose and at 15, 30, 45, 60, 90, 120 and 180 minutes post-dose and then hourly up to 5 hours post-dose.

P On CAM2038 q1w dosing days (i.e., Days 0 and 7), vital signs will be collected at pre-dose and at 15, 30, and 60 minutes post-dose, then hourly up to 6 hours post-dose.

	Screening	Inpatie	Inpatient Qualification Phase			Inpatient Treatment Phase				
Visit:	1				2					
Day:	-39 to -11	-10, -9, -8, -7, OR -6	-9, -8, -7, -6, OR -5 to -4	-3 to -1	0	1 to 3 & 4 to 6	7	8 to 10 & 11 to 13	14/ ET	21
Adverse Events q	X	X	X	X	X	X	X	X	X	X
C-SSRS (baseline/screening)	X									
C-SSRS (since last visit) r			X		X		X		X	
MADRS s	X		X		X		X		X	
COWSt	X	X	X	X	Xu	X	X u	X	X	
oows				X	Xu	X	X u	X	X	
CAM2038 Injection Site Examination					X	X	X	X	X	
Oral IR Morphine 30 mg Dosing v		X	X	X						
CAM2038 q1w SC Injection w					X		X			

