Randomization will be used to avoid bias in the assignment of treatment for all the Hydromorphone Challenge Sessions and in the assignment of subjects to the 24 mg or 32 mg CAM2038 q1w dose groups during the Treatment Phase. Prior to the Qualification/Baseline Hydromorphone Challenge Session, subjects will be randomized to 1 of 6 challenge sequences, according to two 3 x 3 William squares (ABC, ACB, BAC, BCA, CAB, CBA), and will receive one dose of hydromorphone daily over 3 consecutive days, including 2 doses of hydromorphone and 1 dose of placebo. This approach has previously been shown to be sensitive to identifying dose-related agonist effects, while ensuring that both subjects and staff remain blinded to the dose of hydromorphone or placebo being administered, thereby reducing the risk of potential expectancy effects. As an additional precaution, subjects will be housed in inpatient research units for the duration of the study both for safety monitoring and to ensure that the subjects do not use other illicit opioids while enrolled in the study, as this may affect the Hydromorphone Challenge Session results.

Randomization increases the likelihood that known and unknown subject attributes (e.g., demographics and baseline characteristics) will be evenly balanced across dose groups and enhance the validity of statistical comparisons across dose groups. It was not possible to include a placebo control group (CAM2038 SC Placebo injection) in the current study because the enrolled population will be physically dependent on opioids and would go into opioid withdrawal with placebo administration. Therefore, this study includes a Qualification/Baseline Hydromorphone Challenge Session to establish the frequency and magnitude of changes in clinical endpoints that may occur in the absence of CAM2038 q1w.

Version: 2.0, 17NOV2015 Page 43 of 99

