# 12.3. Statistical Analyses

Unless otherwise indicated, all testing of statistical significance will be 2-sided, and a difference resulting in a P value of less than or equal to 0.05 will be considered statistically significant.

Version: 2.0, 17NOV2015 Page 70 of 99

Furthermore, the baseline will be the last assessment before the first dosing of the study medication.

Summary statistics will be provided for the variables described in the following sections. For continuous variables, these statistics will typically include the number of subjects, mean, standard deviation (SD), median, minimum, and maximum. For categorical variables, these statistics will typically include the number and percentage of subjects in each category.

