Following the 3-day Qualification/Baseline Hydromorphone Challenge Session (Days -3 to -1), eligible subjects will be randomized in a 1:1 ratio to one of 2 groups to receive CAM2038 q1w at doses of 24 mg or 32 mg, stratified by gender. Subjects will receive two, once weekly injections of CAM2038 q1w, 7 days apart, (injections on Day 0 and Day 7) and will remain inpatient in the CRU for a total of approximately 3 weeks, during which time, 1 qualification/baseline Hydromorphone Challenge session will occur prior to CAM2038 administration then 4 Hydromorphone Challenge Sessions (3 consecutive days each with dose randomized) will be conducted on Days 1 to 3, Day 4 to 6, Days 8 to 10, and Days 11 to 13 after the first CAM2038 administration. Each Hydromorphone Challenge Session will consist of 3 doses of hydromorphone 10 mg/mL IM injections (doses of 0 mg [placebo], 6 mg and 18 mg) administered on 3 consecutive days in randomized order. Eligible subjects will be randomized in a 1:1:1:1:1:1 ratio to 1 of 6 treatment sequences according to two 3×3 William squares. The following treatment sequences will be used: ABC, ACB, BAC, BCA, CAB, and CBA, where A, B, and C are IM hydromorphone doses, 0 mg (placebo), 6 mg, and 18 mg, respectively. The doses, 0 mg (placebo), 6 mg or 18 mg, will be administered once daily during the hydromorphone challenge sessions. Safety assessments will be conducted immediately following each dose of hydromorphone administered in each Challenge Session and scheduled pharmacodynamic evaluations will occur over approximately 5 hours post dose. Plasma BPN and norbuprenorphine (NorBPN) levels will also be obtained approximately 60 minutes prior to hydromorphone dosing (predose) on each day of the Hydromorphone Challenge Sessions.

Subjects will be discharged on Day 14 and a follow-up phone interview will be conducted on Day 21. The degree of hydromorphone dose tolerability will be determined based on the site-specific study Investigator's review of the subject's oximetry data, vital signs, behavior, and physical demeanor.

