11.3 LABORATORY ASSESSMENTS

Chemistry, Hematology, Urinalysis and Coagulation Profile will be assessed at baseline and Week 24 (see Section 10.4.3 for a complete list of parameters to be assessed). Summary statistics for these parameters will be presented by visit for the actual value and change from baseline for each test in each laboratory category (Hematology, Chemistry, Urinalysis, and Coagulation Profile). Shift tables will be presented for shifts from baseline lab categories to end of study laboratory category. The three laboratory categories will be: L (below lower bound of normal range), N (within normal range), and H (above higher bound of normal range).

If a lab value is reported using a non-numeric qualifier (e.g., less than (<) a certain value, or greater than (>) a certain value), the given numeric value will be used in the summary statistics, ignoring the non-numeric qualifier.

If a subject has repeated laboratory values for a given time point, the value from the first evaluation at that time point will be used for summarization purposes. For the purpose of determining baseline, the last nonmissing observation on or prior to randomization will be used. The Week 24 values will be the last post-baseline value on or prior to Week 24.

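### The SAP baseline rule is not limited to pre-dose readings, so post-injection vital signs can become the reference for change from baseline

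*SAP*

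**What the plan says.** **The baseline rules**

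- SAP 6.1 allows for exceptions stated elsewhere and then gives two definitions. The first is that "the last observed measurement prior to or on the date of randomization will be considered the baseline measurement". The second is: "If multiple observations are made during baseline, the baseline will be defined as average of the observations obtained during the baseline phase". The baseline phase is not defined.
- Protocol 12.3 says that "the baseline will be the last assessment before the first dosing of the study medication". It does not name the drug meant, and Protocol 9.2 lists hydromorphone and morphine beside CAM2038 among the investigational products.
- SAP 11.3 has a rule for laboratory tests only: "the last nonmissing observation on or prior to randomization will be used".

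**Randomization and first dose**

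- There are two randomizations. The one to challenge sequence comes early (Protocol 7.2): "Prior to the Qualification/Baseline Hydromorphone Challenge Session, subjects will be randomized to 1 of 6 challenge sequences". The one to CAM2038 dose comes after the Day -3 to -1 session, when "eligible subjects will be randomized in a 1:1 ratio to one of 2 groups" (SAP 4.3). Neither document fixes its calendar day, and SAP 6.1 does not say which randomization it means.
- CAM2038 is first given on Day 0 at about 9:00 am (Protocol 7.1.3.1): "On the morning of Day 0 of the Treatment Phase, subjects will receive one of the following treatments".

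**Vital-sign schedule (Protocol Table 4 footnotes)**

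- On challenge days, including Days -3, -2 and -1: pre-dose; 15, 30, 45, 60, 90, 120 and 180 minutes; then hourly to 5 hours.
- On CAM2038 dosing days, "vital signs will be collected at pre-dose and at 15, 30, and 60 minutes post-dose, then hourly up to 6 hours post-dose".

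**Where baseline is used.** SAP 11.6 and Protocol 12.3.4.3 summarize vital signs as values and as change from baseline. SAP Appendix A lists change-from-baseline tables for COWS and OOWS.

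**The concern.** A baseline for a safety summary should precede the drug whose effect is being described. SAP 6.1 works by calendar date, or by an unnamed phase, and so can admit readings taken after an opioid injection. If the reference has already been moved by hydromorphone or CAM2038, a later change in the same direction looks smaller than it was.

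The measure most exposed is respiratory rate. Safety and tolerability of CAM2038 given with hydromorphone is a stated objective, and Protocol 10.6.1 names respiratory depression among the more serious side effects. The rule is also ambiguous: two programmers following SAP 6.1 could derive different baselines from the same data.

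**Working it through.** The plan states no figure on this point to reproduce. The check applies SAP 6.1 literally to the Table 4 vital-sign schedule.

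**Step 1. Readings per day.**

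- Challenge day: 1 pre-dose, plus 9 post-dose at 15, 30, 45, 60, 90, 120, 180, 240 and 300 minutes = 10.
- Day 0: 1 pre-dose, plus 8 post-dose at 15, 30 and 60 minutes and 2, 3, 4, 5 and 6 hours = 9.

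These are the Table 4 vital-sign sets only. The respiratory-rate checks before morphine doses (Protocol 10.4.5.1) are not counted.

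**Step 2. Last-value rule.**

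| CAM2038 randomization dated | Last scheduled set that day |
|---|---|
| Day -1 | 5 hours after hydromorphone or placebo |
| Day 0 | 6 hours after CAM2038 |

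Neither is a pre-dose reading.

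**Step 3. Averaging rule.** The phase is undefined, so several spans are shown.

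- Days -3 to -1: 3 × 10 = 30 sets. Post-injection: 3 × 9 = 27 (90%). After active hydromorphone: 2 × 9 = 18 (60%). The other 9 post-injection sets follow placebo.
- Days -3 to 0: 30 + 9 = 39 sets. Post-injection: 27 + 8 = 35 (90%). After active hydromorphone or CAM2038: 18 + 8 = 26 (67%).
- Screening to Day -1, assuming 2 to 9 earlier readings: 27/32 = 84% down to 27/39 = 69% post-injection.

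**Step 4. Protocol rule for comparison.** With study medication read as CAM2038, Protocol 12.3 selects the Day 0 pre-dose set. No post-CAM2038 reading enters, and none from the 5-hour windows after hydromorphone.

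**Step 5. Other measures.**

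- COWS and OOWS are given before hydromorphone on challenge days, and the routine Day 0 COWS is before CAM2038. Post-CAM2038 scores arise before baseline only in subjects scored 4-hourly for precipitated withdrawal on Day 0. They enter only if randomization is dated Day 0 or the baseline phase includes Day 0.
- ECG, C-SSRS and MADRS on Day 0 are scheduled before dosing.
- Laboratory tests are scheduled at Screening, check-in and Day 14 or early termination only.

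**Step 6. What attenuation could look like.** The documents give no vital-sign effect size, so this is illustration under assumptions. Let the true fall in respiratory rate be D = 4 breaths/min.

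- Last value at 6 hours after CAM2038, carrying a fraction f of the later effect: reported fall = D × (1 − f). For f = 0.25, 0.52 and 1, this gives 3.0, 1.9 and 0. The middle value borrows the 32 mg concentration ratio from Protocol Table 1, 2.61/5.00 ng/mL at 6 and 24 hours. A concentration ratio in healthy subjects under naltrexone blockade is not an effect ratio.
- Averaging Days -3 to -1, with 60% of sets after active hydromorphone and a mean hydromorphone fall of h: reported fall = D − 0.6 × h. For h = 1, 2 and 3, this gives 3.4, 2.8 and 2.2.

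**The case against.** The case for leaving this alone has real substance.

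- **Change is not the only display.** Vital-sign values are summarized beside the change and are listed by subject. Oxygen saturation below 95% is to be recorded as an adverse event (Protocol 10.4.7), and no formal safety comparison is planned. This stands: a poor baseline distorts one descriptive column and does not hide the raw readings.
- **The SAP may refine the protocol.** Protocol section 12 permits it, and Protocol 12.3 is itself vague about which drug it means. This also stands. The difference alone is not the fault; the fault is that the SAP wording, if followed, gives a post-dose reference.
- **The Day 0 route is conditional.** No passage dates randomization to Day 0. That is correct, but a Day -1 date still selects a reading taken after hydromorphone or placebo.

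A reader might also infer more than the documents support:

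- *That SAP 6.1 and 11.3 contradict each other.* Section 6.1 allows exceptions, 11.3 is one, and no laboratory sample is scheduled on Days -3 to 0.
- *That COWS and OOWS baselines are generally drug-affected.* The routine scores are taken before dosing; only the narrow case in Step 5 is exposed.
- *That safety changes would be cancelled out.* The zero in Step 6 needs full carry-over at 6 hours, which is an assumption and not a finding.

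**Conclusion.** The concern holds for vital signs. As written, SAP 6.1 either selects a post-injection set under both plausible dates of CAM2038 randomization (Day -1 or Day 0), or averages a pool in which 27 of 30 sets over Days -3 to -1 are post-injection, 18 of them after active hydromorphone. Descriptive change from baseline in respiratory rate, blood pressure, pulse and other vital signs can be attenuated. The mechanism and the share of post-dose readings follow from the documents; the amount of attenuation does not.

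This rests on reading randomization in SAP 6.1 as the assignment to CAM2038 dose, dated Day -1 or Day 0, and on the schedule being followed. Entry of post-CAM2038 values further requires a Day 0 date or a baseline phase that includes Day 0.

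The primary result is untouched, because SAP 9.1.1 takes Emax as the maximum post-dose Drug Liking score and uses no baseline. Scheduled laboratory tests, ECG, C-SSRS and MADRS are not exposed to post-CAM2038 values. The point is worth correcting before database lock, but it does not threaten the trial's main conclusion.

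**What to change.** Replace both definitions in SAP 6.1 with one rule: unless otherwise stated, baseline is the last non-missing value before the first CAM2038 injection on Day 0, judged by date and time, with no averaging. Delete the reference to a baseline phase. State that CAM2038 is the study medication meant in Protocol 12.3, so that the two documents agree. SAP 11.3 needs no change.

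Optionally, also show challenge-day vital signs as change from that day's pre-hydromorphone reading, which separates the hydromorphone effect from the CAM2038 effect.

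The cost is SAP wording and a matching derivation in the programs. The Day 0 pre-dose vital signs and COWS are already scheduled, so no new data are needed. There is one small downside. The Day 0 pre-dose reference is taken after at least 12 hours without morphine, in subjects required to have a COWS score of at least 8. It therefore reflects mild withdrawal, and a footnote to the change-from-baseline tables should say so.

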6.2 SOFTWARE

Analyses will be conducted using SAS Version 9.2 or higher.

6.3 CHANGES TO PLANNED ANALYSES

Draft versions of the SAP will be numbered sequentially as Version 0.0i. The final approved version will be numbered as Version 1.00. Revisions after the “Final” version will be numbered as Version 1.0x. The Clinical Study Report will document any changes made after the final version approved before data base lock and treatment unblinding.

7.0 DESCRIPTION OF THE STUDY POPULATIONS

All tables, figures, and listings must include a population descriptor (e.g., ITT, Safety or Completer) in the title.

7.1 DISPOSITION

Subject disposition summaries will be presented by treatment arm (CAM2038 q1w 24 mg and CAM2038 q1w 32 mg) and sequence (ABC, ACB, BAC, BCA, CAB, and CBA) and will include the number of subjects randomized, the number and percentage of randomized subjects in each of the predefined populations, as well as the number and percentage of subjects who complete the study. The summaries will also include the reasons for early discontinuation from the study.

Disposition summaries will be presented for each of the predefined populations separately.

7.2 DEMOGRAPHIC AND BASELINE CHARACTERISTICS

A summary of demographics and baseline characteristics will be presented by treatment arm, sequence, and overall for the ITT, Completer and safety populations. The demographic characteristics will consist of age, sex, ethnicity, and race using descriptive statistics.

Demographic data including age, race, ethnicity, and gender, as well as baseline clinical characteristics will be summarized. Age will be calculated based on the following conditional algorithm:

- Has the patient had his/her birthday this year?
 - Yes, then AGE = (year of informed consent) – (year of birth).
 - No, then AGE = (year of informed consent) – (year of birth) – 1.

Clinical baseline characteristics summarized will include, if available, BW, BMI, type of primary opioid use (heroin, prescription opioid pain relievers, other), years of drug use, when first diagnosed with opioid dependence, proportion of patients previously treated for opioid dependence, duration of buprenorphine treatment, duration of 8 mg or less buprenorphine treatment, and dose of buprenorphine treatment prior to randomization. Clinical baseline characteristics will be summarized by treatment group, sequence, and overall.

